3 PROTOCOL/AMENDMENT NO.: 007-04

DOCUMENT HISTORY

Document	Date of Issue	Overall Rationale
Amendment 04	14-DEC-2022	To add a test of the efficacy hypothesis at the interim analysis and to reduce the study power.
Amendment 03	23-JUN-2022	Canada-specific amendment created to fulfill health authority request.
Amendment 02	06-APR-2022	Germany-specific amendment created to fulfill health authority request.
Amendment 01	08-MAR-2022	To update an inclusion criterion and provide sites with additional screening time to identify suitable participants for this study.
Original Protocol	12-JAN-2021	Not applicable

PROTOCOL AMENDMENT SUMMARY OF CHANGES

Amendment: 4

Overall Rationale for the Amendments:

To add a test of the efficacy hypothesis at the interim analysis and to reduce the study power.

Summary of Changes Table:

Section # and Name	Description of Change	Brief Rationale
1.2 Schema	Added a test of the efficacy hypothesis at	To permit the study to stop early for efficacy.
1.3 Schedule of Activities	the interim analysis.	
4.1 Overall Design		
4.4.1 Clinical Criteria for Early Study Termination		
9.1 Statistical Analysis Plan Summary		
9.6 Statistical Methods		
9.7 Interim Analyses		
9.8 Multiplicity		
9.9.1 Efficacy		
10.1.4.2 External DMC		
10.8 Appendix 8: PK Substudy		
9.9 Sample Size and Power Calculations	Reduced the study power to 80%.	To allow study completion within reasonable timelines due to slower than expected efficacy event accrual.

Section # and Name	Description of Change	Brief Rationale
 1.1 Synopsis 3 Hypotheses, Objectives, and Endpoints 4.2.1.1 Efficacy Endpoints 9.4.1 Efficacy Endpoints 9.6.1.2 Secondary Efficacy Endpoints 	Updated the secondary objective from 'reducing the number of AVG thrombosis events' to 'increasing the time to each AVG thrombosis event (first and recurrent)' and the statistical analysis.	The Andersen-Gill model will be used to analyze the time to each AVG thrombosis event (first and recurrent).
1.3 Schedule of Activities	Added reference to Section 6.4 Study Intervention Compliance.	Consultation between the investigator and Sponsor is required for study interruptions >4 consecutive doses.
	Added note for vital status assessment.	A participant's vital status should be assessed whenever in question.
	Added note for FSH assessment.	FSH is assessed to confirm postmenopausal status.
2.1 Study Rationale	Updated background on clinical trials for FXI inhibitors.	New clinical study data became available.
2.2.2 Preclinical and Clinical Studies	Updated description of Study P004.	Study P004 was completed.
2.3 Benefit/Risk Assessment	Updated section with data from the current Investigator's Brochure.	Study P004 was completed and new clinical study data became available.
3 Hypotheses, Objectives, and Endpoints	Updated the endpoints for evaluation of exposure-response or dose-response of MK-2060 QW for AVG thrombosis events.	To clarify that pharmacokinetic endpoints will be collected (steady state C_{max} and C_{trough})

Section # and Name	Description of Change	Brief Rationale	
4.1 Overall Design 4.2.1.1 Efficacy Endpoints	Death was added to the list of events needing adjudication.	To adjudicate all deaths, including deaths that are not captured within the secondary safety endpoint (ie, major bleed) or the	
9.6.2 Analysis Methods for Safety Analyses		exploratory efficacy endpoint (major thrombotic cardiovascular event).	
10.1.4.3 Clinical Adjudication Committee			
4.1 Overall Design	Added statement regarding censoring	To avoid including in the analysis events	
9.6.1.1 Primary Efficacy Endpoint	kidney transplant events in the primary efficacy analysis and safety analyses.	(both efficacy and safety) occurring in participants who underwent kidney	
9.6.2 Analysis Methods for Safety Analyses		transplant, which could confound the results.	
4.3.1 Starting Dose for This Study	Removed paragraph related to ongoing Study P004	Study P004 was completed.	
5.2 Exclusion Criteria	Exclusion criterion #7 was revised.	To clarify that regular use of aspirin in doses >150 mg per day is prohibited and to	
6.5 Concomitant Therapy	Added aspirin in doses >150 mg per day to the list of prohibited medications.	allow the use of periprocedural heparin, low-dose heparin for DVT prophylaxis while hospitalized, and topical NSAIDs.	
6.1 Study Intervention(s) Administered	Updated the NIMP definition to NIMP/AxMP	To align with EU CTR.	
6.3.2 Stratification	Added note to clarify the 'aspirin use' stratification criterion.	'As needed' aspirin use is not included in the stratification criterion.	

Section # and Name	Description of Change	Brief Rationale
6.4 Study Intervention Compliance	Revised the statement regarding the management of participants with study intervention interruptions.	To clarify which study intervention interruptions require consultation between the investigator and Sponsor.
7.1 Discontinuation of Study Intervention	Added discontinuation criterion for participants with prolonged study intervention interruptions and clarification for participant reloading.	To provide the option to maintain participants in the study after a prolonged study intervention interruption (>4 consecutive doses).
8.2 Efficacy Assessments	Revised statement regarding PRO questionnaire administration.	To clarify that the PRO questionnaires are administered by the interviewer (investigator or qualified designee).
8.11.6 Premature Discontinuation Visit	Added time frame for the Safety Follow- up Visit for discontinued participants who continue to be monitored in the trial.	To clarify the timing of the Safety Follow-up Visit.
Title Page Section 10.1.1 Code of Conduct for Clinical Trials Throughout Document	Sponsor entity name and address change.	Merck Sharp & Dohme Corp. underwent an entity name and address change to Merck Sharp & Dohme LLC, Rahway, NJ, USA. This conversion resulted only in an entity name change and update to the address.
Section 10.7 Appendix 7: Country-specific Requirements	Country-specific amendments for Germany and Canada were added to this global amendment. Changes are outlined in Section 10.7 and referenced in Sections 1.3 Schedule of Activities, 5.2 Exclusion Criteria, and 8.3.5.1 Serum Pregnancy Test.	To consolidate country-specific amendments 2 and 3.

PRODUCT: MK-2060

PROTOCOL/AMENDMENT NO.: 007-04

Section # and Name	Description of Change	Brief Rationale
10.9 Appendix 9: Hemostasis	Added information related to an in vivo study of reversal of MK-2060-induced aPTT prolongation by transfusion of FFP in rhesus monkeys. Change is referenced in Section 6.5.2 Surgery Guidance.	To include additional data that may assist study investigators with the management of bleeding events.
Throughout Document	Minor administrative, formatting, grammatical, and/or typographical changes were made throughout the document.	To ensure clarity and accurate interpretation of the intent of the protocol.

Table of Contents

		L AMENDMENT SUMMARY OF CHANGES	
1		OCOL SUMMARY	
•		ynopsis	
	•	chema	
		chedule of Activities	
2		DUCTION	
_		tudy Rationale	
		ackground	
	2.2.1	Pharmaceutical and Therapeutic Background	
	2.2.2	Preclinical and Clinical Studies	
	2.3 B	enefit/Risk Assessment	2 7
3		THESES, OBJECTIVES, AND ENDPOINTS	
4		DESIGN	
	4.1 O	verall Design	30
	4.2 Se	cientific Rationale for Study Design	31
	4.2.1	Rationale for Endpoints	32
	4.	2.1.1 Efficacy Endpoints	32
	4.	2.1.2 Patient-reported Outcomes Endpoints	33
	4.	2.1.3 Safety Endpoints	34
	4.	2.1.4 Pharmacokinetic Endpoints	35
	4.	2.1.5 Immunogenicity Endpoints	35
	4.	2.1.6 Pharmacodynamic Endpoints	35
	4.	2.1.7 Planned Exploratory Biomarker Research	36
		4.2.1.7.1 Planned Genetic Analysis	36
	4.	2.1.8 Future Biomedical Research	36
	4.2.2	Rationale for the Use of Placebo	36
	4.3 Ju	ustification for Dose	37
	4.3.1	Starting Dose for This Study	37
	4.3.2	Maximum Dose/Exposure for This Study	37
	4.3.3	Rationale for Dose Interval and Study Design	38
	4.4 B	eginning and End of Study Definition	
	4.4.1	Clinical Criteria for Early Study Termination	
5		POPULATION	
	5.1 In	nclusion Criteria	39

1 PROTOCOL SUMMARY

1.1 Synopsis

Protocol Title: A Randomized Parallel-group, Placebo-controlled, Double-blind, Event-driven, Multi-center Phase 2 Clinical Outcome Trial of Prevention of Arteriovenous Graft Thrombosis and Safety of MK-2060 in Patients With End Stage Renal Disease Receiving Hemodialysis

Short Title: MK-2060 Global Study in Patients with End Stage Renal Disease Receiving Hemodialysis

Acronym: FXI Hemodialysis Study

Hypotheses, Objectives, and Endpoints:

In adult patients with ESRD receiving hemodialysis via an AVG:

Primary Objectives	Primary Endpoints
- Objective: To evaluate the efficacy of MK-2060 compared to placebo in increasing the time to first arteriovenous graft thrombosis event. Hypothesis: At least 1 of the MK-2060 doses is superior to placebo in increasing the time to first occurrence of arteriovenous graft thrombosis event	- Arteriovenous graft thrombosis events
Secondary Objectives	Secondary Endpoints
- Objective: To evaluate the efficacy of MK-2060 compared to placebo in increasing the time to each arteriovenous graft thrombosis event (first and recurrent).	- Arteriovenous graft thrombosis events
- Objective: To assess the safety and tolerability of MK-2060.	 Adverse events Major bleeding events or clinically relevant non-major bleeding events (per International Society on Thrombosis and Haemostasis criteria) Discontinuation of study intervention due to adverse event(s)

Overall Design:

Study Phase	Phase 2								
Primary Purpose	Prevention								
Indication	Prevention of arteriovenous graft thrombosis								
Population	Patients with ESRD receiving hemodialysis via an arteriovenous graft								
Study Type	Interventional								
Intervention Model	Parallel This is a multi-site study.								
Type of Control	Placebo								
Study Blinding	Double-blind								
Blinding Roles	Sponsor Investigator Care Provider Outcomes Assessor Participants or Subjects								
Estimated Duration of Study	The Sponsor estimates that the study will require approximately 20 months from the time the first participant is enrolled until the last participant's last study-related telephone call or visit.								

Number of Participants:

Approximately 489 participants will be randomized.

Intervention Groups and Duration:

Intervention			 	1			 				
Groups	Intervention Group Name	Drug	Loading Dose Strength	Maintenance Dose Strength	Dose Frequency	Route of Adminis- tration	Regimen/ Treatment Period				
	MK-2060 High Dose	MK-2060	20 mg	20 mg	Loading dose – 1 dose, 3 times during Week 1 QOD. Maintenance dose – 1 dose QW after Week 1	IV	Double- blind treatment period				
	MK-2060 Low Dose	MK-2060	6 mg	6 mg	Loading dose – 1 dose, 3 times during Week 1 QOD. Maintenance dose – 1 dose QW after Week 1	IV	Double- blind treatment period				
	Placebo	Placebo	0 mg	0 mg	Loading dose – 1 dose, 3 times during Week 1 QOD. Maintenance dose – 1 dose QW after Week 1	IV	Double- blind treatment period				
		-	-	; QW= once a v	week. ine hemodialysis so	essions.					
Total Number of Intervention Groups/ Arms	Total 3 Number of Intervention Groups/										
Duration of Participation This is an event-driven study expected to run for approximately 20 more from FPE until LPLV. After a screening period of up to 30 days, eligible participants will be treated with study intervention until full accrual of events, with an expected median treatment duration of 10 months. Participants will be monitored for safety events from the time of provided documented informed consent through the final contact, 3 months after last treatment dose.											

PRODUCT: MK-2060 PROTOCOL/AMENDMENT NO.: 007-04

Study Governance Committees:

Executive Oversight Committee	Yes									
Data Monitoring Committee	Yes									
Clinical Adjudication Committee	Yes									
Study governance considerations are outlined in Appendix 1.										

[figure not shown]
Study Accepts Healthy Volunteers: No

A list of abbreviations used in this document can be found in Appendix 10.

1.2 Schema

The study design is depicted in Figure 1.

Figure 1 Study Design

AVG= arteriovenous graft; ESRD= end-stage renal disease; FP= first patient; LPLV= last patient last visit; QOD= every other day; QW= once a week; R= randomization; V= visit.

Note: FP randomized to LPLV will be approximately 20 months.

1.3 Schedule of Activities

Study Period	Scree	ening					Т	reatme	nt Perio	od	Premature Intervention Discontinuation						Notes
Visit Number/Title	1 Screen	2 Rand	3	4	5	6	7	8	9	Visit n	Final Efficacy Visit	Safety Follow-up Visit	Premature Discon. Visit	Safety Follow-up Visit	Visit n	Final Efficacy Visit	
Scheduled Days/Month	Day -30 to Day 1	Day 1	Day 3	Day 5	Day 8	Day 15	Day 29	Day 57	Day 85	Every 3 months	Based on Efficacy Cutoff date ^a	3 months after Final Efficacy Visit	Study Intervention Discon.	3 months after Discon.	Every 3 months	Based on Efficacy Cutoff date ^a	
Visit Window			±1 day	±1 day	±1 day	±3 days	±3 days	±5 days	±7 days	±7 days		±7 days	±7 days	±7 days	±7 days		Refer to Section 6.4.
Administrative Procedures																	
Informed Consent	X																
Informed Consent for Future Biomedical Research	X																
Informed Consent for PK Substudy	X																
Informed Consent for QoL Questionnaires	X																At preselected sites
Inclusion/ Exclusion Criteria	X	X															
Participant Identification Card	X	X															Add randomization number to card on Day 1
Medical History	X																
Identification of External Contact Person	X																For vital status assessment
Prior/Concomitant Medication Review	X	X	X	X	X	X	X	X	X	X	X	X	X	X	X	X	
Treatment/ Randomization Number		X															
Study intervention Administration		X	X	X	X	int	erventi dy duri	on to b	e admii ılarly s	oses, study nistered cheduled ons							See Section 8.1.8 for details.

PRODUCT: MK-2060

PROTOCOL/AMENDMENT NO.: 007-04

Study Period	Scree	ning		Treatment Period Premature Intervention Discontinuation									Notes				
Visit Number/Title	1 Screen	2 Rand	3	4	5	6	7	8	9	Visit n	Final Efficacy Visit	Safety Follow-up Visit	Premature Discon. Visit	Safety Follow-up Visit	Visit n	Final Efficacy Visit	
Scheduled Days/Month	Day -30 to Day 1	Day 1	Day 3	Day 5	Day 8	Day 15	Day 29	Day 57	Day 85	Every 3 months	Based on Efficacy Cutoff date ^a	3 months after Final Efficacy Visit	Study Intervention Discon.	3 months after Discon.	Every 3 months	Based on Efficacy Cutoff date ^a	
Visit Window			±1 day	±1 day	±1 day	±3 days	±3 days	±5 days	±7 days	±7 days		±7 days	±7 days	±7 days	±7 days		Refer to Section 6.4.
Clinical Procedures	/Assessm	ents															
Full Physical Examination	X										X		X			X	
Systemic Infusion Reaction Assessment		X	X	Х													Any infusion reaction must be reported as an AE
Height	X																
Weight	X	X			X	X	X	X	X	X	X	X	X	X	X	X	Post-dialysis
Directed Physical Examination		X				X	X		X	X							
Vital Signs	X	X	X	X	X	X	X	X	X	X	X	X	X	X	X	X	Pre-dialysis. BP and HR to be measured in triplicate.
12-lead ECG	X										X		X			X	
Clinical Events Assessment		X	X	X	X	X	X	X	X	X	X	X	X	X	X	X	Collection of events for selected endpoints
Vital Status Assessment			Х	X	X	X	X	X	X	X	X	Х	X	X	X	X	Assessed whenever participant's vital status is in question.
AE/SAE Review	Х	X	X	X	X	X	X	X	X	X	X	X	X	X	X	X	Participants should be trained to contact the site to report AEs as soon as they occur
KDQOL-SF & EQ- 5D-5L Questionnaires		X								X	X		X				At preselected sites every 6 months
Central Laboratory	Assessn	ents										_					
Serum FSH – (WOCBP only)	X	X ^b															To confirm postmenopausal status.
Pregnancy test (Serum) in WOCBP	Xc						X	X	X	X			X				Germany-specific requirements are in Appendix 7

Study Period	Scree	ening					Т	reatme	nt Perio	od			Prematur	e Interventio	n Discontir	nuation	Notes
Visit Number/Title	1 Screen	2 Rand	3	4	5	6	7	8	9	Visit n	Final Efficacy Visit	Safety Follow-up Visit	Premature Discon. Visit	Safety Follow-up Visit	Visit n	Final Efficacy Visit	
Scheduled Days/Month	Day -30 to Day 1	Day 1	Day 3	Day 5	Day 8	Day 15	Day 29	Day 57	Day 85	Every 3 months	Based on Efficacy Cutoff date ^a	3 months after Final Efficacy Visit	Study Intervention Discon.	3 months after Discon.	Every 3 months	Based on Efficacy Cutoff date ^a	
Visit Window			±1 day	±1 day	±1 day	±3 days	±3 days	±5 days	±7 days	±7 days		±7 days	±7 days	±7 days	±7 days		Refer to Section 6.4.
Coagulation (INR, PT, aPTT)	X																To be collected separate from hematology laboratory tests
Hematology	X	X	X	X	X	X	X	X	X	X	X		X			X	
Liver Function Tests		X			X	X	X	X	X	X	X		X			X	
Chemistry		X			X	X	X	X	X	X	X		X			X	
Pharmacokinetics/In	mmunog	enicity	/Pharn	nacody	namic	s/ Bion	arkers	5									
Blood for PK evaluation		X ^d			Xe	Xe	Xe		X ^d	Xe	Xe		X ^e				Record date and time of collection. To be collected for all participants in main study.
Blood for ADA		X					X		X	X	X		X				Collect pre-dialysis
Blood for PT/aPTT/FXI Activity		X			X	X	X	X	X	X	X		X				Collect predose (Sections 8.8 and 8.10)
Blood for Genetic Analysis		X								DD			1:				Collect predose from enrolled participants only

ADA= anti-drug antibodies; AE= adverse event; aPTT= activated partial thromboplastin time; BP= blood pressure; Discon= discontinuation; ECG= electrocardiogram; EQ-5D-5L= Euro quality of life 5-dimensional, 5-level questionnaire; FSH= follicle stimulating hormone; FXI= factor XI; KDQOL-SF= kidney disease quality of life questionnaire-short form; PK= pharmacokinetics; QoL= quality of life; SAE= serious adverse event; WOCBP= women of childbearing potential.

Visit n= Starting from Visit 9 (Day 85) all subsequent visits will be scheduled every 3 months until study completion is reached.

- a. Efficacy Cutoff will be declared when the required number of events has accrued for the primary efficacy endpoint (see Section 9.7). If the study stops at IA, the Final Efficacy Visits will be scheduled to occur within 14 days of Sponsor's notification to stop the study. If the study continues, the Final Efficacy Visits will be scheduled to occur in the 14 days following the Final Analysis efficacy cutoff date.
- b. All WOCBP will have an FSH test at Visit 1. Serum FSH at Visit 2 is only required for participants who have less than 1 year of amenorrhea.
- c. A pregnancy test must be performed at Visit 1. In addition, 1 pregnancy test must be performed within 6 days before the first dose of study intervention (see Section 5.1).
- d. Trough and peak sample collection. Trough sample to be collected pre-dialysis **before any IV heparin is administered to the participant**. Peak sample to be collected approximately 30 minutes **after** infusion ends. If dosing and drawing is from the same access point, flush the access point with saline before sample collection. Record the time samples were drawn, time infusion was started, and time the infusion ended.
- e. Trough sample collection only. To be collected pre-dialysis (before any IV heparin is administered to the participant). Record the time the sample was drawn and the time infusion was started.

Note: For sites participating in the PK substudy, see Table 10 – PK Substudy Schedule of Activities.

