The EQ-5D-5L is a generic questionnaire used to assess current health status as reported by patients and will provide data to develop health utilities for use in health economic analyses [Rabin, R. and de Charro, F. 2001]. It consists of 5 domain questions and 1 VAS response. The domain questions assess mobility, self-care, usual activities, pain/discomfort, anxiety/depression, with 5-level response options (no problems, slight problems, moderate problems, severe problems, and extreme problems). Summary scores will be calculated from the 5 domain scores according to scoring instructions from the EuroQol group and the EQ-5D-5L value sets for the US and for Europe. Scores range from 1.00 for perfect health to 0.00 for death. The EQ-5D VAS included in the EQ-5D-5L records patient self-rated health on a 20 cm vertical VAS with endpoints labeled 'the best health you can imagine' and 'the worst health you can imagine' and is scored on a 0 to 100 scale. The EQ-5D-5L is available in over 60 translations with established validity, reliability, and responsiveness

[Pickard, A. S., et al 2007] and is appropriate for a wide range of health conditions and treatments [EuroQol Research Foundation 2019]. It has been used in patients with ESRD and is a valid and sensitive health utility measure in this population [Lee, A. J., et al 2005] [Manns, B. J., et al 2002] [Gerard, K., et al 2004]. Minimally important difference estimates for the EQ-5D utility score range between 0.03 and 0.05 [McClure, N. S., et al 2018]. In cases when a validated translation is needed and not available for a specific language, participants who speak that language will be exempt from the requirement to complete the questionnaire.

The KDQOL-SF and EQ-5D-5L PROs are not pure efficacy or safety endpoints because they are affected by both disease progression and treatment tolerability.

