7 DISCONTINUATION OF STUDY INTERVENTION AND PARTICIPANT WITHDRAWAL

7.1 Discontinuation of Study Intervention

Discontinuation of study intervention does not represent withdrawal from the study.

As certain data on clinical events beyond study intervention discontinuation may be important to the study, they must be collected through the participant's last scheduled follow-up, even if the participant has discontinued study intervention. Therefore, all participants who discontinue study intervention prior to completion of the protocol-specified treatment period will still continue to participate in the study as specified in Section 1.3 and Section 8.11.3, unless the participant has withdrawn from the study (Section 7.2).

Participants may discontinue study intervention at any time for any reason or be discontinued from the study intervention at the discretion of the investigator should any untoward effect occur. In addition, a participant may be discontinued from study intervention by the investigator or the Sponsor if study intervention is inappropriate, the study plan is violated, or for administrative and/or other safety reasons. Specific details regarding procedures to be performed at study intervention discontinuation are provided in Section 8.1.9 and Section 8.11.6.

A participant must be discontinued from study intervention but continue to be monitored in the study for any of the following reasons:

- 1. The participant or participant's legally acceptable representative requests to discontinue study intervention.
- 2. The participant has a confirmed positive serum pregnancy test.
- 3. Upon site learning the participant will undergo a kidney transplant during the study.
- 4. The participant has a major non-traumatic bleed.
- 5. The participant has a medical condition or personal circumstance that, in the opinion of the investigator and/or Sponsor, places the participant at unnecessary risk through continued participation in the study, while on study treatment, or does not allow the participant to adhere to the requirements of the protocol.
- 6. The participant requires ongoing treatment with a prohibited medication (Section 6.5).
- 7. The participant permanently transitions from AVG to an alternative hemodialysis access.

PRODUCT: MK-2060

PROTOCOL/AMENDMENT NO.: 007-04

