8.3.6 Quality of Life Questionnaires

At preselected sites, the KDQOL-SF and the EQ-5D-5L questionnaires will be administered by the interviewer (investigator or qualified designee) at the visits specified in the SoA (Section 1.3). The questionnaires should be administered before administration of study intervention.

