8.11.4 Final Efficacy Visit

The Final Efficacy Visit will be conducted for all participants once the planned number of AVG thrombosis events is observed and the efficacy cutoff is declared by the Sponsor.

If applicable, participants will continue in the study until the Final Efficacy Visit but will no longer be administered study intervention at this visit or going forward. Participants who prematurely discontinued study intervention are required to attend the Final Efficacy Visit for collection of clinical events and all assessments and procedures outlined in the SoA.

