8.11.6 Premature Discontinuation Visit

At the Discontinuation Visit, all laboratory testing and procedures outlined in the SoA will be completed. Discontinuation Visit procedures will be performed on participants as soon as possible after discontinuing study intervention (\leq 7 days).

All participants who discontinue study intervention prior to completion of the protocol-specified treatment period will continue to attend all remaining protocol-specified visits, including the Safety Follow-up Visit, which is completed approximately 3 months from the date of last dose of study medication, and perform all procedures stipulated in the SoA. In the

69

PRODUCT: MK-2060

PROTOCOL/AMENDMENT NO.: 007-04

event a participant specifically withdraws consent for further follow-up, no additional information is permitted to be collected.

If the participant does not attend the Discontinuation Visit, a telephone contact for collection of protocol-defined endpoint events should occur. In such cases, the phone contact will not be considered a protocol deviation. If the site is unable to reach the participant, the site will contact the 'external contact person' identified by the participant during screening to collect participant's vital status (Section 8.1.12).

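### KDQOL-SF and EQ-5D-5L are not collected after the Premature Discontinuation Visit, although participants who stop study intervention keep attending study visits

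*Combined protocol and SAP*

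**What the plan says.** In Section 1.3 the questionnaire row carries the note "At preselected sites every 6 months". Its marks fall at Randomization, at Visit n and the Final Efficacy Visit of the treatment period, and at the Premature Discontinuation Visit. The three columns that follow for participants who stopped early (Safety Follow-up, Visit n every 3 months, Final Efficacy Visit) are empty. Sections 8.2 and 8.3.6 refer back to this schedule for timing and add no later assessment.

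These participants are still in the study. Section 7.1 says they "will still continue to participate in the study as specified in Section 1.3 and Section 8.11.3". Section 8.11.6 says they "will continue to attend all remaining protocol-specified visits". Section 8.11.4 adds: "Participants who prematurely discontinued study intervention are required to attend the Final Efficacy Visit".

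Two of the mandatory reasons for stopping in Section 7.1 are "The participant has a major non-traumatic bleed" (item 4) and "The participant permanently transitions from AVG to an alternative hemodialysis access" (item 7).

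Section 3 lists, among the exploratory objectives, the effect of MK-2060 versus placebo on health-related quality of life and the characterisation of health utilities. Section 9.4.2 defines the endpoints as change from baseline over time. Section 4.2.1.2 says the two instruments "are not pure efficacy or safety endpoints because they are affected by both disease progression and treatment tolerability".

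**The concern.** The protocol expects these instruments to respond to disease progression and to tolerability. Permanent loss of the graft as access is a consequence of the event the drug is meant to prevent, and a major bleed is the main safety concern. Each forces a stop, and collection ends at the visit that records the stop. If MK-2060 prevents access loss or causes bleeding, the share of participants without later questionnaires will differ by arm, and the missing values belong to participants whose quality of life is most likely to have changed.

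At stake is how the exploratory quality-of-life comparison and the utilities for health economic work can be interpreted. The supplemental SAP may specify a missing-data model, but it cannot recover assessments the schedule never collects. Any model would rest on assumptions that the trial's own data could not test.

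**Working it through.** **1. Is the gap real, or a table-extraction artefact?** Split on its column stops, the questionnaire row has 17 cells: 16 visit columns and the notes. The haematology, ECG and clinical-events rows also have 17. Haematology and ECG carry a mark in the post-discontinuation Final Efficacy column, and clinical events is marked in all three post-discontinuation columns. A column shift does not explain the blanks.

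**2. What is lost per participant?** Assume questionnaires at months 6, 12 and 18 plus the Final Efficacy Visit.

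- Cutoff at month 10 (the expected median treatment duration), stop at month 3: the month-6 and Final Efficacy assessments are lost, with 10 − 3 = 7 months unmeasured.
- Cutoff at month 10, stop at month 8: the Final Efficacy assessment is lost, with 10 − 8 = 2 months unmeasured.
- Cutoff at month 20 (outer bound), stop at month 3: months 6, 12, 18 and Final Efficacy are lost, with 20 − 3 = 17 months unmeasured.

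Every early discontinuer still in the study at cutoff loses at least the Final Efficacy assessment.

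**3. How large could the effect on the comparison be?** The plan gives no discontinuation rate and no figure of its own to reproduce, so this is an illustration.

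From the documents: the registry rate of 69.4 thrombotic access failures per 100 patient-years (Section 4.2), λ = 0.694 per year for placebo; HR 0.6 (Section 9.9.1), so 0.694 × 0.6 = 0.4164 for MK-2060; the quoted minimally important difference of 0.03-0.05 (Section 4.2.1.2).

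Assumed: a thrombosis leads to permanent access loss with probability p = 0.2 to 0.6; follow-up is uniform on 3 to 17 months (median 10), so a = 0.25 and b = 1.4167 years; utility falls by 0.10 after access loss, none of it recorded.

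With a constant thrombosis hazard, access loss has hazard k = λp, and the expected share lost by the end of follow-up is

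1 − [exp(−ka) − exp(−kb)] / [k(b − a)].

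For placebo with p = 0.2, k = 0.694 × 0.2 = 0.1388 and the share is 1 − (0.9659 − 0.8215)/(0.1388 × 1.1667) = 0.108.

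| p | Placebo lost | MK-2060 lost | Difference | × 0.10 |
|---|---|---|---|---|
| 0.2 | 10.8% | 6.7% | 4.2 points | 0.004 |
| 0.4 | 20.3% | 12.8% | 7.5 points | 0.007 |
| 0.6 | 28.6% | 18.5% | 10.1 points | 0.010 |
| 0.6, hazard doubled after a first thrombosis (simulated) | 31% | 20% | 11 points | 0.011 |

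The placebo mean alone would be overstated by 0.108 × 0.10 = 0.01 up to 0.31 × 0.10 = 0.03. The treatment comparison would miss 0.004 to 0.011. In the simulation, median unmeasured time after access loss was about 5 months.

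For the hidden between-arm difference to reach 0.03 even in the last row, the utility drop would have to be about 0.03/0.11 = 0.27. Bleeding is not quantified, because the documents give no expected rate of major bleeds.

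**The case against.** The strongest reply is that little depends on this. The endpoints are exploratory, carry no hypothesis or power, and are collected only at preselected sites. The primary, secondary and safety analyses do not use them. That stands, and it limits the point to an inexpensive improvement.

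Four stronger readings are tempting, and the documents do not support them.

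- *Quality of life is never observed after graft loss or a bleed.* One assessment is taken at the Premature Discontinuation Visit, within 7 days of stopping, and for item 7 that would ordinarily follow the change of access. What is missing is everything later. A participant whose thrombosis is treated and who stays on study intervention keeps the 6-monthly schedule. A clinically relevant non-major bleed prompts interruption (Section 6.5.1) and is not a listed mandatory stop.
- *The analysis set is an on-treatment survivor sample.* Section 9.5.2 analyses participants as randomized and needs a baseline and one post-baseline assessment. The discontinuation assessment qualifies, so those who stop are included, with truncated data.
- *The schedule contradicts the treatment-policy strategy.* Section 9.6.1 sets that strategy for the primary efficacy estimand only. No estimand is stated for quality of life, and methods for exploratory objectives are left to the supplemental SAP.
- *The bias reaches the minimally important difference.* The 0.03 is the error in one arm's mean, not in the comparison.

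The magnitude is also soft. The access-loss share and the 0.10 drop have no source in the documents. The calculation ignores whatever the discontinuation assessment captures, and Amendment 04 reports event accrual slower than expected, so the registry rate probably runs high.

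Finally, simply pooling all assessments would bring post-transplant quality of life into the comparison, because a planned kidney transplant is also a mandatory stop (item 3) and the efficacy analyses censor at transplant. The fix has to deal with that.

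**Conclusion.** The gap holds as a matter of reading the schedule: no questionnaire is planned after the Premature Discontinuation Visit, although participants must attend later visits where it could be given. Because two of the mandatory stops lie on the pathways through which treatment could change quality of life, the missingness is plausibly informative and may differ by arm.

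Its reach is limited to the exploratory quality-of-life and utility objectives at preselected sites. Under the assumptions shown, access loss hides about 0.004 to 0.011 of between-arm utility difference, below the quoted 0.03-0.05; the contribution of bleeding is unknown. The structural gap does not depend on those assumptions, but the size does. The change is worth making because it is cheap and missed assessments cannot be collected afterwards, not because a trial conclusion is at risk.

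**What to change.** 1. In the Section 1.3 questionnaire row, mark KDQOL-SF and EQ-5D-5L in the premature-discontinuation block at Visit n (same 6-month spacing) and at the Final Efficacy Visit.
2. State in the supplemental SAP that summaries of these endpoints use all assessments regardless of study intervention status, with an on-treatment summary as supportive.
3. State that assessments after a kidney transplant are handled as in the efficacy analyses, by censoring at the transplant date.
4. Since Section 7.1 allows telephone follow-up of clinical events for those who do not attend, say whether the interview may be done that way or is recorded as missed with a reason.

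The cost is interviewer and participant time: about 16 minutes for the 80-item KDQOL-SF, plus the EQ-5D-5L, at visits already required and only at preselected sites. No visit is added, and dosing, blinding, alpha and sample size are untouched.
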